10. EFFICACY VARIABLES

The primary efficacy variable for dosage selection is the percent reduction in spleen volume from baseline as measured by MRI or CT at Weeks 12 and 24.

Other supportive measures for evaluation as part of the dose-response relationship include

- the percentage of patients who achieve at least 35% reduction in spleen volume
- % TSS reduction from baseline, and
- the percentage of patients with at least 50% reduction in TSS.

The planned analyses for the efficacy endpoints of the study are detailed in the subsections below and will be performed in the full analysis set.

10.1 Spleen volume (SPV)

Spleen volume will be measured by MRI (preferred) at baseline and Weeks 12 and 24 or end of treatment visit if imaging did not occur at the end of Week 24. Unscheduled imaging assessments may be performed at physician discretion if he/she considers disease-related symptoms to be worsening. Patients who cannot undergo MRI, or for whom MRI is not available will assess spleen volume by CT scan. However, for each patient, the same imagining modality will be used throughout the study. An independent radiologist, blinded to all patient and site identifiers as well as treatment assignments, will measure spleen volume. While images generated as part of unscheduled visits may be read locally if treatment discontinuation is being considered, only the scheduled centrally read images will be used for the efficacy analysis.

The percent reduction and the proportion of subjects with a $\geq 35\%$ spleen volume reduction will be computed as follows:

$$\text{SPV \% Reduction} = - \left(\frac{\text{Week 12 or 24 SPV} - \text{Baseline SPV}}{\text{Baseline SPV}} \right) * 100$$

$$\text{Proportion of subject with SPV reduction} \geq 35\% = \left(\frac{\text{Number of subjects with} \geq 35\% \text{ SPV reduction}}{\text{Number of subjects in the FAS population}} \right)$$

10.2 Total Symptom Score (TSS)

The MPN-SAF TSS 2.0 is an instrument measuring disease impact among patients with Myelofibrosis (MF). Supportive measures of efficacy are the percent change from baseline in TSS as measured by the MPN-SAF TSS 2.0 and the proportion of patients with TSS reduction $\geq 50\%$ at Weeks 12 and 24. Patients will begin reporting symptoms via electronic diary at least 7 days before starting pacritinib treatment and will continue until the Week 48 visit. After Week 48, patients will complete a 7-day recall version of the symptom assessment at each study visit.

TSS Algorithm

- **The daily TSS** is the sum of the scores for the following symptoms: tiredness, early satiety, abdominal discomfort, night sweats, pruritus, bone pain, and pain under ribs on the left side (excludes the inactivity score).
- **The baseline TSS** is the mean of the daily TSS over the 7 consecutive days prior to the start of treatment. Missing values during these days are handled as described below (section 7.2.2).
- **Week 24 TSS** is the mean of the daily TSS obtained during the 28 consecutive days prior to the post-baseline spleen volume scan date (i.e. Week 12 or 24 visit date if scan date is

missing). A similar approach will be performed when defining the TSS values for Weeks 12, 36 and 48.

- The percent reduction in TSS from baseline to the Week 12 or 24 visit is computed by:

$$\text{TSS \% Reduction} = - \left(\frac{\text{Week 12 or 24 TSS} - \text{Baseline TSS}}{\text{Baseline TSS}} \right) * 100.$$

Handling of Missing TSS Values

- If any of the seven individual symptoms scores are missing, the TSS for that day will be considered as missing.
- The baseline TSS is set to missing if fewer than 4 daily TSS are available out of the 7 consecutive days prior to the start of study treatment.
- The Week 24 TSS is set to missing if fewer than 20 daily TSS are available out of the 28 consecutive days prior to Week 24 spleen volume scan date (or Week 24 visit date if scan date is missing). In sensitivity analyses where Week 24 TSS is derived from the mean of 7 consecutive days of daily TSS, the Week 24 TSS is set to missing if fewer than 4 daily TSS are available out of the 7 consecutive days prior to Week 24 spleen volume scan date (or Week 24 visit date if scan date is missing). Missing TSS at other post-baseline time-points is similarly handled. A similar approach will be performed when defining the TSS values for Weeks 12, 36 and 48.

10.3 Patient Global Impression Assessment

The self-reported measure Patient Global Impression of Change (PGIC) is a 7 point scale depicting a patient's rating of overall improvement. Patients rate their change as 'very much improved', 'much improved', 'minimally improved', 'no change', 'minimally worse' or 'very much worse'. PGIC will be collected at the end of Week 12, the end of Week 24 or the end of treatment visit and every 3 months up to 2.5 years.

10.4 Spleen Length Reduction

Spleen size, assessed by physical examination as the distance below the lower costal margin at the midclavicular line, will be evaluated at study visits Week4, Week 12, Week 24 and every 3 months thereafter up to 2.5 years. The percent change from baseline and the proportion of patients with >50% spleen length (SPL) reduction at 12 and 24 weeks will be computed as follows:

$$\text{SPL \% Reduction} = - \left(\frac{\text{Week 12 or 24 SPL} - \text{Baseline SPL}}{\text{Baseline SPL}} \right) * 100$$

$$\text{Proportion of subject with SPL reduction} \geq 50\% = \left(\frac{\text{Number of subjects with} \geq 50\% \text{ SPL reduction}}{\text{Number of subjects in the FAS population}} \right)$$

10.5 Transfusions

10.6.1 Frequency of Red Blood Cell (RBC) Transfusions

The frequency of RBC transfusions at baseline is defined as the number of units of RBC transfusions per month prior to and including the date of the start of treatment. Since this data comes from two different sources, the baseline RBC transfusion frequency is computed as the sum of the number of units of RBC transfusions in the 90 days prior to the informed consent date and the number of units of RBC transfusions after the informed consent date through to the start of treatment date, divided by the number of days from informed consent to the start of treatment plus 90 days, multiplied by a conversion factor of 30 days/month. That is,

$$\frac{(\# \text{ units from Transfusion History} + \# \text{ units from IC to start of treatment})}{(90 + (\text{treatment start date} - \text{IC date} + 1)) \text{ days}} \times 30 \frac{\text{days}}{\text{month}}.$$

At post-baseline timepoints, the frequency of RBC transfusions is defined as the number of units of RBC transfusions per month in the three months (approximately 84 – 90 days) preceding the visit date. That is,

$$\frac{(\# \text{ units in the days preceding the visit date})}{\text{number of study days from previous visit}} \times 30 \frac{\text{days}}{\text{month}}$$

10.6.2 Frequency of Platelet Transfusions

The frequency of platelet transfusions at baseline is defined as the number of platelet transfusions per month prior to and including the date of the start of treatment. Since this data comes from two different sources, the baseline platelet transfusion frequency is computed as the sum of the number of transfusions in the 90 days prior to the informed consent date and the number of transfusions after the informed consent date through to the start of treatment date, divided by the number of days from informed consent to the start of treatment plus 90 days, multiplied by a conversion factor of 30 days/month. That is,

$$\frac{(\# \text{ transfusions in Transfusion History} + \# \text{ transfusions from IC to start of treatment})}{(90 + (\text{treatment start date} - \text{IC date} + 1)) \text{ days}} \times 30 \frac{\text{days}}{\text{month}}.$$

At post-baseline timepoints, frequency of platelet transfusions is defined as the number of platelet transfusions in the month (30 days) preceding the visit date.

$$\frac{(\# \text{ units in the days preceding the visit date})}{\text{number of study days from previous visit}} \times 30 \frac{\text{days}}{\text{month}}$$

10.7 ECOG Performance Status

The ECOG (developed by the Eastern Cooperative Oncology Group) is scale which describes a patient's level of functioning in terms of their ability to care for themselves, daily activity, and physical ability (walking, working, etc.). It is a scale from 0 to 5 defined as:

GRADE	ECOG PERFORMANCE STATUS
0	Fully active, able to carry on all pre-disease performance without restriction
1	Restricted in physically strenuous activity but ambulatory and able to carry out work of a light or sedentary nature, e.g., light house work, office work
2	Ambulatory and capable of all selfcare but unable to carry out any work activities; up and about more than 50% of waking hours
3	Capable of only limited selfcare; confined to bed or chair more than 50% of waking hours
4	Completely disabled; cannot carry on any selfcare; totally confined to bed or chair
5	Dead

11 SAFETY VARIABLES

11.1 ADVERSE EVENTS

An adverse event (AE) is any untoward medical occurrence in a patient or clinical investigation subject administered a pharmaceutical product and which does not necessarily have to have a causal relationship with this treatment. All AEs, including serious adverse events (SAEs) will be collected during the clinical study from the time the patient signs the informed consent through 30 days following the last dose of study treatment. For screened patients who are not randomized, only

SAEs occurring between the time of informed consent and determination of screen failure are to be reported.

A TEAE is defined as an adverse event (AE) occurring after the first dose of study treatment and within 30 days after the last study treatment date. In addition, an AE with a missing start date but with an end date after the first study drug dose date is also considered a TEAE. An AE occurring after the first dose of study drug that also occurred prior to the first dose of study drug is only considered a TEAE if the AE worsened in grade after the first dose of study drug.

Analysis of AEs will be based on Treatment Emergent Adverse Events (TEAEs).

11.2 SAFETY LABORATORY ASSESSMENTS

Hematology and coagulation function laboratory measures will be collected via central lab, but in addition can be analyzed locally for assessment and management of patients in real time.

11.2.1 HEMATOLOGY

Hematology parameters including CBC, differential, platelet count and hemoglobin A1C among others will be evaluated at screening, baseline, the end of week 4, the end of Week 12, the end of Week 24 or the end of treatment visit, every 3 months during the follow-up period, and 30 days after the last dose of study treatment.

11.2.2 COAGULATION FUNCTION

Coagulation testing will include PT, INR, PTT and TT at screening, baseline, the end of week 4, the end of Week 12, the end of Week 24 or the end of treatment visit, every 3 months during the follow up period, and 30 days after the last dose of study treatment.

11.2.3 CHEMISTRY

Screening laboratory assessments should be performed at least 1 week after the end of prior therapy. Serum chemistry parameters (ALT/SGPT and AST/SGOT, alkaline phosphatase, bilirubin [total, direct, and indirect], creatinine, lactate dehydrogenase (LDH), sodium, potassium, chloride, bicarbonate, calcium, phosphate, magnesium, blood urea nitrogen (BUN/area), albumin, amylase, lipase, glucose, cholesterol, uric acid, and high specificity CRP) will be evaluated by a central laboratory at screening, at baseline and whenever is clinically indicated.

The derived visit window definitions for clinical hematology, chemistry, and coagulation function are displayed in Table 5.

Table 5. Analysis Window Definitions for Clinical Hematology and Coagulation Function Results

Visit	Nominal Day	Range
Baseline	1 (first dose date)	[-14, 1]
Week 4	28	[2, 55]
Week 12	84	[56, 111]
Week 24	168	[112, 195]
Week 36	252	[196, 279]
Week 48	336	[280, 363]
⋮	⋮	⋮
Week XX	XX times 7	[(Week XX-1 upper range + 1, (XX times 7) + 27]
EOT	Last dose date	[Last dose date, Last dose date + 15]
30 days post EOT	Last dose date + 30 days	[Last dose date + 16,]

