¹ Screening procedures must be completed between Days -35 and -7, before treatment initiation, with the exception of the screening (baseline) MRI or CT scan, which must be parformed between Days -10 and -4								
² Day 1 assessments are required to be performed prior to initiation of study treatment and can be performed up to 24 hours prior to initiation of study treatment. At the baseline visit, all patients will be provided with a prescription (and instructions to fill that prescription) for loperamide (Imodium) or a similarly effective antidiarrheal drug. Patients will be instructed to start taking the prescribed loperamide or other antidiarrheal drug per package and physician instructions as soon as they notice any change in frequency or consistency of bowel movements after starting study treatment.								
³ The study visit at week 4 has a scheduling window of ±3 days; however, all procedures other than MRI or CT should be performed on the same day's visit within ±24 hours. ⁴ The study visits at weeks 12 and 24 have a scheduling window of ±7 days; however, all procedures other than MRI or CT should be performed on the same day's visit within ±24 hours.								

Table 1. PAC203 Study Assessments Calendar²⁰

- ⁵ The End of Treatment visit is scheduled within 7 days after terminating study treatment. A final visit to assess events is scheduled 30 ±3 days after the last dose of study treatment. If treatment ends at a regularly scheduled visit, these procedures may be performed at that time.
- ⁶ Informed consent must be obtained before any study-specific washout. This may require 2 weeks (A 2-week washout will be required for anticoagulation agents, antiplatelet agents (except aspirin doses of ≤ 100 mg/day), strong CYP3A4 inhibitors, strong CYP450 inducers, and QTc prolonging agents) or 28 days if patient was taking any experimental therapies. Patients not requiring washout may sign the Informed Consent Form at any time prior to screening procedures.
- ⁷ Vital signs include blood pressure, pulse, respiratory rate, temperature, and body weight.
- ⁸ Height should be measured only at baseline. Spleen size assessed by physical examination as the distance below the LCM at the midclavicular line.

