- ⁹ A single 12-lead ECG (collected in triplicate) will be performed at screening and *within* 1 hour prior to dosing and *at* 4 hours (± 10 minutes) post dosing on Day 1 of week 1 and at the end of weeks 4, 12, and 24, 30 days postterm, and as clinically indicated. ECGs will also be collected pre-dose during the post 24-week follow-up visits within 1 hour prior to dosing. The ECGs will be read centrally by blinded independent cardiologist.
- ¹⁰ Hematology includes CBC, differential, platelet count and hemoglobin A1C. For patients with baseline platelet count of \leq 50,000/µL, platelet count will be monitored weekly for the first 8 weeks, then monthly if counts remain \leq 50,000/µL. These platelet counts must be analyzed by the central laboratory, but local laboratory test results may be used for assessment and management of patients in real time. Samples collected for local testing must also be submitted to the central laboratory and the results captured in the clinical database. Additional hematology testing should be done as clinically indicated.
- Eligibility may be based on local or central laboratory values. Central serum chemistry values will include: ALT/SGPT, AST/SGOT, alkaline phosphatase, bilirubin (total, direct, and indirect) creatinine, LDH, sodium, potassium, chloride, bicarbonate, calcium, phosphate, magnesium, BUN/urea, albumin, amylase, lipase, glucose, cholesterol, uric acid, and high sensitivity CRP. Any samples collected at any visits must be analyzed by the central laboratory, although local laboratories may additionally be used for patient assessment and management in real time.
- ¹² All women of child-bearing potential (WOCBP) must have a pregnancy test at screening. For WOCBP in the UK, the screening pregnancy test must occur no longer than 7 days before the first study drug administration and again at the End of Week 4 visit. Additional pregnancy tests every 12 weeks while on study treatment may be mandated as a country-specific requirement.

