7.1.2.2 Hematology

Hematology parameters including CBC, differential, platelet count, and hemoglobin A1C will be evaluated at screening, baseline, the end of week 4, the end of Week 12, the end of Week 24 or the end of treatment visit, every 3 months during the follow up period, and 30 days after the last dose of study treatment. In addition, for patients with baseline platelet count of $\leq 50,000/\mu$ L, the platelet count will be monitored weekly by the central laboratory for the first 8 weeks, then monthly if counts remain $\leq 50,000/\mu$ L. Samples collected at any visits for platelet counts must be submitted to the central laboratory for analysis, but in addition can be analyzed locally for assessment and management of patients in real time. Additional platelet count testing should be done as clinically indicated.

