13.2 CLINICAL LABORATORY MEASUREMENTS

The counts and percentages of the shifts in CTCAE grade from baseline to the worst and last post-baseline grade (not including the 30 post treatment end visit in the evaluation of worst grade at post-baseline) will be presented for each laboratory measure. Descriptive statistics of change and percent change from baseline in laboratory values will be presented by visit. Plots of the shift from baseline to worst post-baseline in selected parameters by treatment arm will be presented. In the case of hemoglobin, a parameter that is hugely affected by transfusions, the percent change over time will be explored in patients who did not have a transfusion in the 90 days prior to informed consent or on study.

Laboratory results (including serum pregnancy) will be provided in a subject list and include at minimum subject id, age, treatment arm, visit, assessment date, laboratory category, laboratory parameter, results and lab units.

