13.3.3 VITAL SIGN MEASUREMENTS

Descriptive statistics (mean, median, standard deviation, minimum, and maximum) of the actual values and the change from baseline in vital sign measurements, including weight, will be presented by visit.

A table summarizing clinically notable blood pressure and weight measurements which are aligned with CTCAE cut-offs, where available, will be displayed. The proportion of subjects whose worst observed values while on study treatment (on or after the first day of treatment) meet the following clinically notable criteria will be tabulated by treatment arm:

- Systolic Blood Pressure
 - < 85 mm Hg
 - $\geq 140 - < 160$ mm Hg
 - ≥ 160 mm Hg

- Diastolic Blood Pressure
 - < 50 mm Hg
 - ≥ 90 - < 100 mm Hg
 - ≥ 100 mm Hg
- Weight gain from baseline
 - $\geq 5\%$ - < 10% increase
 - $\geq 10\%$ - < 20% increase
 - $\geq 20\%$ increase
- Weight loss from baseline
 - $\geq 5\%$ - < 10% decrease
 - $\geq 10\%$ - < 20% decrease
 - $\geq 20\%$ decrease

The derived visit window definitions for vital signs are displayed in Table 6.

Table 6. Analysis Window Definitions for Vital Signs Results

Visit	Nominal Day	Range
Baseline	1 (first dose date)	[-14, 1]
Week 4	28	[2, 55]
Week 12	84	[56, 111]
Week 24	168	[112, 195]
Week 36	252	[196, 279]
Week 48	336	[280, 363]
⋮	⋮	⋮
Week XX	XX times 7	[(Week XX-1 upper range + 1, (XX times 7) + 27]
EOT	Last dose date	[Last dose date, Last dose date + 15]
30 days post EOT	Last dose date + 30 days	[Last dose date + 16,]

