17 DATA HANDLING RULES

17.1 Definition of Baseline Value

The baseline value for safety analyses will be defined as the last assessment prior to the start of treatment, unless otherwise specified.

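### SAP Tables 5 and 6: from Week 24 the visit windows run -56/+27 days, overlap the end-of-treatment row without precedence, and have no rule for repeat values

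*SAP*

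**What the plan says.** SAP 11.2.3 sets the laboratory windows: "The derived visit window definitions for clinical hematology, chemistry, and coagulation function are displayed in Table 5". The post-baseline rows are Week 4, Days 2-55; Week 12, Days 56-111; Week 24, Days 112-195; Week 36, Days 196-279; Week 48, Days 280-363. The general row reads "Week XX-1 upper range + 1, (XX times 7) + 27". An end-of-treatment (EOT) row covers the last dose date to 15 days later, and a post-treatment row starts on day 16 after the last dose and has no upper limit. SAP 13.3.3 uses the same limits for vital signs: "The derived visit window definitions for vital signs are displayed in Table 6".

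SAP 13.2 applies the laboratory windows: "Descriptive statistics of change and percent change from baseline in laboratory values will be presented by visit". The one selection rule for safety values concerns baseline (SAP 17.1): "The baseline value for safety analyses will be defined as the last assessment prior to the start of treatment, unless otherwise specified". For ECGs, SAP 11.2.4 averages the triplicate QTcF readings. For several laboratory values in one window the SAP gives no rule.

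Patients with baseline platelets at or below 50,000/µL are sampled more often. Under Protocol 7.1.2.2 their platelets are "monitored weekly by the central laboratory for the first 8 weeks, then monthly if counts remain" at or below that level. Footnote 10 to Protocol Table 1 brings locally tested samples in as well: "Samples collected for local testing must also be submitted to the central laboratory and the results captured in the clinical database". Footnote 4 to the same table fixes the scheduled visits: "The study visits at weeks 12 and 24 have a scheduling window of ±7 days".

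**The concern.** A visit window should attach a sample to the visit it is nearest to, and each patient should count once per visit. Tables 5 and 6 depart from the first aim from Week 24 on and say nothing about the second.

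The group most exposed is the lowest platelet stratum, whose extra counts come at times that other patients are not sampled. By-visit platelet change is supportive evidence on dose-related thrombocytopenia in a dose-finding trial. If values from Day 112 sit in the Week 24 column, or one patient contributes seven values to Week 4 and another contributes one, the by-visit table no longer describes a defined group at a defined time. The outcome would then depend on a programming choice that the SAP does not record.

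**Working it through.** **1. Reproduce the plan's limits.** Inputs: nominal days 28, 84, 168, 252 and 336, and the general row of Table 5. Upper limit = 7 × week + 27; lower limit = previous upper limit + 1.

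| Visit | Lower | Upper | Days before / after nominal |
|---|---|---|---|
| Week 4 | 2 | 28 + 27 = 55 | 26 / 27 |
| Week 12 | 56 | 84 + 27 = 111 | 28 / 27 |
| Week 24 | 112 | 168 + 27 = 195 | 56 / 27 |
| Week 36 | 196 | 252 + 27 = 279 | 56 / 27 |
| Week 48 | 280 | 336 + 27 = 363 | 56 / 27 |

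All five match Table 5.

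**2. Compare with nearest-visit limits.** Midpoints: (28 + 84)/2 = 56; (84 + 168)/2 = 126; (168 + 252)/2 = 210; (252 + 336)/2 = 294. With ties going to the later visit, the windows are Week 4, 2-55; Week 12, 56-125; Week 24, 126-209; Week 36, 210-293. The addition of 27 days is right only where visits are 56 days apart. For 84-day gaps the matching addition is 84/2 - 1 = 41.

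- Days 112-125 are labelled Week 24 but are nearer Week 12.
- Days 196-209 are labelled Week 36 but are nearer Week 24.
- Days 280-293 are labelled Week 48 but are nearer Week 36.

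Each run is 14 days. In the Week 24 window that is 14 of 195 - 112 + 1 = 84 days. For comparison, the SAP's efficacy window for Week 24 is symmetric, Days 147-189.

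**3. Who has samples on those days.** Weekly draws end about Day 56. Monthly draws every 28 days then fall on Days 84, 112, 140 and 168. The second is 112 - 84 = 28 days from Week 12 and 168 - 112 = 56 days from Week 24, yet is called Week 24. If weekly draws end on Day 56 or 57 and the spacing is 28 or 30 days, the second monthly draw falls on Day 112, 113, 116 or 117, always in the mislabelled run.

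Scheduled visits are safe: Week 4 (±3 days) is Days 25-31, Week 12 is Days 77-91 and Week 24 is Days 161-175, all inside the right window.

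**4. Overlap with the EOT row.** Take a last dose on Day 115. The EOT row covers Days 115-130, and the EOT visit is due within 7 days, by Day 122. Days 115-122 also lie in the Week 24 row (112-195). Nothing says which label applies.

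**5. Repeat values in Week 4.** Weekly draws on Days 7, 14, ..., 56 put seven in Days 2-55 and the eighth in Week 12. If draws run 1 to 3 days early, all eight fall in Week 4. Other patients have one scheduled count there. The Week 4 limits already equal the midpoints, so this is a matter of repeat records, not of a misplaced boundary.

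If every record were pooled, and a share p of patients were in the low-platelet stratum, that stratum would supply 7p/(7p + 1 - p) of the Week 4 counts. The documents do not give p. Assuming 20%, one third and 50% gives 1.4/2.2 = 64%, 2.33/3.00 = 78% and 3.5/4.0 = 88%. With one value per patient the share is p and no misweighting arises.

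**The case against.** The strongest reply is that the SAP nowhere says that all records in a window enter the mean. SAP 6.1 lists the number of observations among its summary statistics, but as a convention for every continuous variable. A by-visit change table is compatible with one value per patient. That stands: what the documents show is a missing rule, not a bias.

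A reader might go further and infer that the Week 4 platelet fall would be reported at about half its size. One can produce such a figure: with one third of patients in the stratum, assumed changes of -5 there and -30 elsewhere (×1,000/µL) give a patient mean of -21.7 and a pooled mean of -10.6. Both changes are invented, and pooling is itself an assumption. With equal changes in the two groups the means agree. Protocol 1.3.4 reports that many patients' platelets were stable or rose. The documents do not support a size for this effect.

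A reader might also infer that early stoppers are counted at Week 24 as if treated to then. Tables 5 and 6 have an EOT row for them, so this is not established; only the lack of precedence is.

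Reach is narrow too. The weekly and monthly schedule covers platelet counts in one stratum. Vital signs and coagulation have no such schedule, and chemistry after baseline is drawn only when clinically indicated, so these are exposed through EOT or unscheduled samples. Randomization is stratified at the same platelet cut-off, so the extra scheduled counts should be roughly balanced across arms. That is a fair limit, though not a complete one: the special cases after Protocol Table 1 allow extra visits after dose modification for toxicity, which can differ by dose.

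Finally, safety windows need not match efficacy windows. Agreed; the efficacy window serves here only as a comparison.

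**Conclusion.** The point holds for by-visit laboratory and vital-sign summaries. Three things follow from the documents without further assumption: 14-day runs before Weeks 24, 36 and 48 carry the label of the more distant visit; the EOT row overlaps the visit rows with no precedence; and no rule picks among repeat values in a window. For patients who remain at or below 50,000/µL the mislabelling is routine, since the second monthly count lands in Days 112-125 under the regular spacings tried. Misweighting of platelet means is conditional on pooling, and its size cannot be derived from the documents.

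These defects do not reach scheduled Week 4, 12 and 24 visits. Nor do they reach the primary safety measure or the worst-grade shifts, which use each patient's grade and not a by-visit mean. The change is worth making because the by-visit platelet table supports the dose comparison, but the dose choice does not rest on it alone.

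**What to change.** 1. In Tables 5 and 6 set the limits at midpoints: Week 4, Days 2-55 (unchanged); Week 12, Days 56-125; Week 24, Days 126-209; Week 36, Days 210-293; and so on. In the general row, replace 27 by 41 for visits followed by a 12-week gap.
2. State that by-visit summaries use one value per patient per window: the value closest to the nominal day, with the scheduled visit preferred. Midpoint limits alone would leave the seven weekly counts in Week 4, so this sentence is needed separately.
3. State whether the EOT or the visit label takes precedence when a sample meets both. Midpoint limits do not remove the overlap: a Day 115 EOT sample would then also meet the Week 12 definition. The same sentence should cover the open-ended post-treatment row.
4. Keep all records that SAP 13.2 now admits for worst-grade shifts, and all records for grade ≥4 thrombocytopenia and anemia.

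The cost is SAP wording and a record-selection step in the programs. No new data are needed, and the worst-grade and grade ≥4 analyses stay as planned.
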